9.4.1 Stopping Rules

The study will be monitored to ensure that the mortality within 30-days after the procedure does not substantially exceed an anticipated rate. We anticipate the rate of 30-day mortality is 10% or less and determine the stopping rule by a Bayesian approach ¹³. The stopping boundary is reached if the posterior probability that the 30-day mortality rate exceeds 10% is at least 90%. We take our prior distribution to be a beta distribution so that our prior clinical opinion is worth 20% of the weight we will place on the new data. This gives the prior parameters $a = 0.3$, $b = 2.7$. Hence when we make decisions about stopping the study, the data from the study will dominate over the prior opinion.

The following table summarizes the threshold numbers for the stop rule boundary, which would lead to a recommendation to stop the study due to the excess 30-day mortality.

Number of subjects	Stop if the number of deaths within 30 days reaches
2-5	2
6-11	3
12-15	4

We investigated the performance of the above stopping rule by a simulation study. In each simulation run, we generated a study with 15 independent Bernoulli trials, each with a true certain 30-day mortality, and compared these outcomes with the above stopping boundary to determine whether the study was stopped. We repeated the simulation 100,000 times and computed the proportion of stopped studies using the above stopping rule. The following table summarizes the performance of this stopping rule:

True 30-day mortality rate	2.5%	5%	10%	15%	20%	25%	30%	35%
Proportion of Stopped Studies (%)	0.7	3.1	13.8	30.4	48.6	65.5	78.6	88
Average number of subjects (n)	14.9	14.7	13.8	12.5	11	9.5	8.1	6.9
Average number of 30-day mortality (n)	0.4	0.7	1.4	1.9	2.2	2.4	2.4	2.4

These simulation results suggest that our stopping rule has a low probability of stopping a study when the true 30-day mortality rate is 10% or less, and the probability of stopping a study is high when the true 30-day mortality rate exceeds 10%. There, we believe that our stopping rule for 30-day mortality has satisfactory statistical properties.

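### Minor: Section 9.4.1 calls the chance of stopping high whenever true 30-day mortality exceeds 10%, but its own correct table gives 30.4% at 15% and 48.6% at 20%

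*Combined protocol and SAP*

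**What the plan says.** Section 9.4.1 sets out to ensure that "the mortality within 30-days after the procedure does not substantially exceed an anticipated rate". Its benchmark is stated plainly: "We anticipate the rate of 30-day mortality is 10% or less". The criterion is Bayesian: "The stopping boundary is reached if the posterior probability that the 30-day mortality rate exceeds 10% is at least 90"%. With a Beta(0.3, 2.7) prior this becomes a table of death counts: 2 deaths among 2 to 5 subjects, 3 among 6 to 11, and 4 among 12 to 15.

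Performance was assessed with 100,000 simulated trials: "we generated a study with 15 independent Bernoulli trials, each with a true certain 30-day mortality". The proportions stopped are printed for eight true mortality rates.

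The section then draws a two-part conclusion. Stopping is said to be unlikely when true mortality is 10% or less, and "the probability of stopping a study is high when the true 30-day mortality rate exceeds 10"%. From this it infers that "we believe that our stopping rule for 30-day mortality has satisfactory statistical properties".

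**The concern.** The second part of the conclusion covers every true rate above 10% without qualification. The table immediately above it shows fewer than half of trials stopping at both 15% and 20%. A reader who takes the sentence at its word would overrate the protection that the rule gives when true mortality lies between 10% and about 20%.

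This matters because the rule is the only numerical mortality boundary in the protocol, for a device that Section 9.1 says has not been used in humans before. The sentence is also the stated ground for finding the rule satisfactory.

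**Working it through.** **Inputs, all from Section 9.4.1.** Prior Beta(0.3, 2.7); stop when the posterior probability that the rate exceeds 10% is at least 0.90; at most 15 subjects; the printed boundary; the printed stopping proportions.

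**Step 1: the boundary.** After k deaths in n subjects the posterior is Beta(0.3 + k, 2.7 + n − k). The boundary is the smallest k with P(rate > 0.10) ≥ 0.90. The values where it changes are:

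| n | k | P(rate > 10%) | Stop? |
|---|---|---|---|
| 1 | 1 | 0.8488 | no |
| 2 | 2 | 0.9743 | yes |
| 5 | 2 | 0.9071 | yes |
| 6 | 2 | 0.8784 | no |
| 6 | 3 | 0.9783 | yes |
| 11 | 3 | 0.9082 | yes |
| 12 | 3 | 0.8886 | no |
| 12 | 4 | 0.9716 | yes |
| 15 | 4 | 0.9429 | yes |

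This gives 2 deaths for n = 2 to 5, 3 for 6 to 11 and 4 for 12 to 15, exactly as printed.

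**Step 2: a formula for the chance of stopping.** Deaths accumulate and the boundary is constant within each block. A trial checked after every subject therefore runs to completion only if there are at most 1 death in the first 5 subjects, at most 2 in the first 11 and at most 3 in all 15. Let A, B and C be independent binomial death counts in blocks of 5, 6 and 4 subjects with true rate p. Then

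P(stop) = 1 − Σ P(A + B = j, A ≤ 1) × P(C ≤ 3 − j), summed over j = 0, 1, 2.

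**Step 3: worked at p = 0.20.**
- A: P(0) = 0.3277, P(1) = 0.4096.
- B: P(0) = 0.2621, P(1) = 0.3932, P(2) = 0.2458.
- j = 0: 0.3277 × 0.2621 = 0.0859.
- j = 1: 0.3277 × 0.3932 + 0.4096 × 0.2621 = 0.2362.
- j = 2: 0.3277 × 0.2458 + 0.4096 × 0.3932 = 0.2416.
- C: P(≤ 3) = 0.9984, P(≤ 2) = 0.9728, P(≤ 1) = 0.8192.
- P(not stopped) = 0.0859 × 0.9984 + 0.2362 × 0.9728 + 0.2416 × 0.8192 = 0.0858 + 0.2298 + 0.1979 = 0.5135.
- P(stop) = 1 − 0.5135 = 0.4865, against 48.6% printed.

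At p = 0.15 the three terms are 0.1673, 0.3210 and 0.2088. They sum to 0.6970, so P(stop) = 0.3030, against 30.4% printed.

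**Step 4: the whole curve.**

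| True rate | Printed (%) | Exact (%) |
|---|---|---|
| 2.5% | 0.7 | 0.73 |
| 5% | 3.1 | 3.21 |
| 10% | 13.8 | 13.89 |
| 12.5% | not printed | 21.60 |
| 15% | 30.4 | 30.30 |
| 20% | 48.6 | 48.65 |
| 25% | 65.5 | 65.50 |
| 30% | 78.6 | 78.85 |
| 35% | 88 | 88.18 |

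The largest difference is 78.85 − 78.6 = 0.25 percentage points. The printed average numbers of subjects and deaths also reproduce to rounding; at 20%, for example, the exact values are 11.05 and 2.21, printed as 11 and 2.2.

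**Step 5: where stopping becomes likely.** Solving P(stop) = t for p gives 20.4% for t = 0.50, 30.5% for t = 0.80 and 36.3% for t = 0.90.

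**The case against.** The best case for leaving the text alone has four parts.

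- **The facts are disclosed.** The full row of stopping proportions sits just above the sentence, so a DSMB, IRB or FDA reader sees both together. No figure is wrong or hidden.
- **The word is qualitative.** The document never defines a high probability, and its aim is to catch a substantial excess. The sentence could be read as a contrast across the table, from 0.7% to 88%. Any rule also has a modest chance of stopping just above its threshold, so the 12.5% figure alone proves little.
- **Nothing operational depends on it.** The rule acts on counts of 2, 3 or 4 deaths. Section 9.4 adds six-monthly DSMB review with power to recommend termination, and IRB power to suspend. Section 10.2.4 requires deaths to be notified to the sponsor within 3 working days. Section 10.3 sends 30-day outcomes to FDA after every 5 subjects.
- **Limited sensitivity is expected with 15 subjects.** Section 9.1 says openly that the number is not statistically derived.

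All four limit the consequence, and they are why the point is graded minor. They do not make the sentence accurate. It refers to any rate above 10%, not to a substantial excess. Even at double the anticipated maximum the chance of stopping is below one half, which no ordinary use of the word covers. A small sample is a reason to state the limitation, not to describe it favourably.

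**Conclusion.** The concern holds, as a minor overstatement. The boundary and the table are right; only the interpretation of the table is wrong. The rule leaves about 70% of trials unstopped at a true rate of 15% (100 − 30.4 = 69.6%) and slightly more than half at 20% (100 − 48.6 = 51.4%). It becomes more likely than not to stop only above about 20%, and reaches an 80% chance only at about 30%.

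These figures rest on the conditions of the document's own simulation: independent outcomes, a constant true rate, 15 subjects, and the boundary checked after every subject with the 30-day outcome known. Checking less often could only lower the chance of detecting a crossing. This is not a finding against the stopping rule itself.

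**What to change.** Keep the first half of the concluding sentence in Section 9.4.1 and replace the second half with the figures already in the table. For example: the rule stops about 14% of studies at a true 30-day mortality of 10%, 30% at 15%, 49% at 20%, 66% at 25%, 79% at 30% and 88% at 35%; it is more likely than not to stop only when true mortality exceeds about 20%.

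Then rest the judgement that the rule is satisfactory on those figures, noting that the limited sensitivity between 10% and 20% follows from a sample of 15.

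The cost is one or two sentences, and the stated performance reads less favourably. The boundary, prior, sample size and oversight arrangements do not change.

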9.5 Off study criteria

- Completion of the 12-month follow-up
- The subject voluntarily withdraws
- Significant subject non-compliance with follow-up visits, despite repeated investigator effort to assure compliance, including baseline counseling and consent, telephone encouragement, and registered letter reminders if necessary. Such non-compliance will be documented and monitored independently.
- Death

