8.1 Data transfer to collaborators

De-identified and de-linked data and images will be transferred to collaborators at Transmural Systems LLC, the manufacturers of the test article. The de-identification assures individual subjects cannot be identified.

Transcatheter valve registry is a nationwide CMS-mandated registry of patients undergoing TAVR. All sites are encouraged to enroll subjects into the TVT registry. TTVT registry numbers will be collected and used for collaboration with the TTVT registry and TAVR device manufacturers such as Edwards Lifesciences. These TTVT registry numbers are linking codes that do not identify subjects. De-identified and de-linked data may be transferred to collaborators at Edwards Lifesciences.

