9.0 BIOSTATISTICAL AND ANALYTICAL CONSIDERATIONS

9.1 Sample Size

The sample size is not statistically derived.

This is an early feasibility study of a device not previously used in humans. An arbitrary initial sample size of 15 is proposed in coordination with the FDA Centers for Devices and Radiologic Health.

Up to 30 subjects will be consented until 15 subjects undergo attempted transcaaval closure using the test article.

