9.2.5 Additional Secondary Endpoints

Additional secondary endpoints include

- Procedure success classifying covered stent implantation as a normal provisional part of the procedure.
- Covered stent implantation at the TCD implantation site
- Acute aorto-caval fistula score at procedure completion ¹²: 0=occlusion, 1=patent fistula, 2=cruciform fistula pattern, 3=extravasation.
- Modified VARC-2 vascular complications ¹² at 30 days
- VARC-2 bleeding complications ¹² at 30 days
- Major adverse cardiovascular events (MACE), defined as VARC-2 Early Safety composite: No mortality, stroke, life-threatening bleeding, AKI stage 2+, major vascular complication, valve-related complication
- Closure success at 30 days and 12 months.
- Mortality, all-cause, cardiovascular vs non-cardiovascular, peri- vs non-periprocedural, related to TCD or not)
- Aorto-caval fistula patency at each timepoint, assessed combining completion angiography and arterial-phase follow-up CT.
- AKIN acute kidney injury
- Freedom from infection related to the TCD at each time point
- Thrombocytopenia < 50,000 attributable to residual aorto-caval fistula or the TCD
- Hemolysis attributable to residual aorto-caval fistula or the TCD
- CT analysis: Device position; Device integrity; Aortocaval fistula patency; Aortocaval tract pseudoaneurysm; Aortic pseudoaneurysm; Retroperitoneal hematoma grade (stranding {=absent and not

- evidence of overt bleeding; } small; moderate; larger); Intracaval mass or thrombus; Aortic dissection and inferred relatedness to TCD (adjacent to access port) or procedure (remote to access port)
- Outcomes of subjects greater than 65 years (i.e. eligible for Medicare based on age), to determine generalizability to the Medicare population¹

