Event	Narrative	Probability	Severity	Risk (Probability x Severity)	Available Evidence to Consider Risk	Conclusion and risk mitigation strategy
Late erosion or migration or unexpected perivascular pathology	There is a theoretical risk of unexpected late complications of caval-aortic access and closure, including device erosion, failure, migration, or late vascular or perivascular remodeling or other pathology.	1	4	4	The adaptive geometry of the Intravascular disk and neck along with compression element and outer PET fabric is designed to conform to aortic pathology and irregular mural rents to achieve hemostasis under a range of anatomies. In addition, outer PET fabric is designed to allow for tissue ingrowth for long-term hemostasis.	This risk is graded as negligible and justified in light of the potential benefit. Risk will be further mitigated by the protocol including CT examinations at each follow up through 1 year to monitor the presence of erosion
Nephrotoxic injury due to additional iodinated radio-contrast during trans caval TAVR and associated follow-up	Iodinated radiocontrast is necessary for X-ray procedures including TAVR. Aortography is performed as part of trans caval access and closure and requires iodinated contrast. This may be offset in part or in whole by iodinated contrast not administered as part of management of large-bore arterial access for conventional TAVR	1	3	3		The risk is rated as negligible. It is considered justified in light of the potential benefit. Risk will further be mitigated with informed consent.
Infection, early or late	Prosthetic implants risk early or late infection	2	4	8	Sterilization and packaging validation results confirm that the product, as packaged, will maintain a sterility assurance level (SAL) of 10^{-6} and that the sterile barrier is maintained through transit. Antimicrobial prophylaxis is a routine component of TAVR performed during the same session as the trans caval access and closure.	This risk is graded as tolerable. It is considered justified in light of the potential benefit. Risk will be further mitigated by the IFU including a precaution for physicians to evaluate the packaging at the time of use and to not use product where the sterile barrier may be compromised. In addition, prophylactic antibiotics will be prescribed per standard TAVR follow up.

KEY LEVEL	1	2	3	4	5
Probability	Rare	Uncommon	Common	Normal	

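### Section 9.5 takes visit non-attenders off study without separating them from consent withdrawals, and nothing requires their vital status or device events to be traced to month 12

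*Combined protocol and SAP*

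**What the plan says.** Section 9.5 gives four ways to leave the study. One is "Completion of the 12-month follow-up"; two others are voluntary withdrawal and death. The fourth is "Significant subject non-compliance with follow-up visits, despite repeated investigator effort to assure compliance". The efforts it names are counseling at baseline, telephone encouragement and, if needed, registered letters. The stated consequence is "Such non-compliance will be documented and monitored independently". Nothing is said about the subject's later outcome, and the term off study is not defined.

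Other sections assume that outcomes are known for a year. Section 10.2.3 runs adverse event recording from day 0 to the 12-month follow-up. Section 9.2.6 has the events committee review deaths and key endpoints in the first year. Section 9.2.3 measures device success at 30 days and 12 months and requires, among other things, survival, the original device in place and no later procedure. Section 9.2.5 adds "Mortality, all-cause, cardiovascular vs non-cardiovascular, peri- vs non-periprocedural, related to TCD or not".

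Section 9.1 describes the setting: "This is an early feasibility study of a device not previously used in humans". Appendix A describes the device as a permanent implant and lists a "theoretical risk of unexpected late complications of caval-aortic access and closure".

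**The concern.** Non-attendance and withdrawal of consent are different events. A subject who stops attending may still accept a telephone call or a records check, but section 9.5 gives both the same status. A site that reads off study in its ordinary sense could stop collecting outcomes on someone who still carries the implant.

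In an elderly, high-risk population, non-attendance may reflect frailty, admission elsewhere or a complication. The documents do not say so, but it is a reasonable worry, because it would make the loss related to outcome. At stake are 12-month device success, mortality, late infection and the adjudicated first-year events. Appendix A also relies on CT through one year to watch for erosion, persistent fistula and vascular injury. A subject taken off study loses that surveillance, and no other outcome check replaces it.

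**Working it through.** **1. Passages side by side.**
- Section 9.5: persistent non-attendance leads to off study; the non-compliance itself is documented.
- Section 10.2.3: adverse events are recorded through 12 months. There is no clause on off-study subjects, either to include or to exclude them.
- Section 10.2.4: the investigator reports a death within 3 working days of being notified. This covers deaths the site hears of and does not require it to look for them.
- Section 9.2.6: the committee works from case report form data, so it sees only what was collected.
- Section 13.7.3: missing data need an explanation. No analysis rule follows.
- Section 9.2: intention-to-treat is defined by attempting transcaval crossing, as-treated by completing closure attempts. Neither set depends on completing follow-up, but how an unknown 12-month outcome is counted is not stated.
- Contact without a visit is already feasible. Section 5.3 allows the 6-month encounter by telephone, section 5.4 leaves continuing care with primary physicians, and section 8.1 says "TTVT registry numbers will be collected and used for collaboration with the TTVT registry", although registry enrollment is only encouraged.

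**2. The plan's own calculation.** The one stated calculation that depends on known vital status is the 30-day mortality rule in section 9.4.1. With a Beta(0.3, 2.7) prior and k deaths in n subjects, the posterior is Beta(0.3 + k, 2.7 + n − k); stop if P(rate > 10%) ≥ 90%. This reproduces the boundary exactly: 2 deaths for n = 2–5, 3 for 6–11, 4 for 12–15. An exact recursion over 15 subjects gives a 13.9% chance of stopping at true mortality of 10% (stated 13.8%) and 48.7% at 20% (stated 48.6%). The plan's figures are sound.

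**3. Weight of one subject.** Section 9.1: "An arbitrary initial sample size of 15 is proposed". One subject is 1/15 = 6.7 percentage points.

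**4. Effect of unknown 12-month outcomes.** The documents give no loss rate; section 7 says only that retention should be high. Losses of 0 to 3 are therefore an assumption. Suppose no late event is seen in the n = 15 − m subjects who are followed. Then:
- range of the true proportion in the 15: 0 to m/15;
- two-sided 95% Clopper-Pearson upper limit if the m are dropped: 1 − 0.025^(1/n);
- chance of seeing at least one event of true rate 10%: 1 − 0.9^n.

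| Unknown (m) | Reported if dropped | Possible in all 15 | 95% upper limit | Chance of ≥1 event |
|---|---|---|---|---|
| 0 | 0/15 | 0% | 21.8% | 79.4% |
| 1 | 0/14 | 0 to 6.7% | 23.2% | 77.1% |
| 2 | 0/13 | 0 to 13.3% | 24.7% | 74.6% |
| 3 | 0/12 | 0 to 20.0% | 26.5% | 71.8% |

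The loss of precision is small. What matters is the third column: the width of what cannot be excluded.

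**5. If the unknowns were also all failures and all dropped.** With 12 true successes in 15 (80%), removing 1, 2 or 3 failures gives 12/14 = 86%, 12/13 = 92% or 12/12 = 100%. This needs two further assumptions: that every lost subject failed, and that lost subjects leave the denominator. If an unconfirmed subject is instead counted as not a success, the result stays 12/15.

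**6. The mortality rule.** It is touched only if a subject is lost before 30-day status is known. As an illustration (assumption), if 10%, 20% or 30% of 30-day deaths went unseen and were counted as survivors, the chance of stopping at true mortality of 20% would fall from 48.7% to 41.3%, 33.9% or 26.7%. Losses after day 30 do not affect it.

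**The case against.** The strongest reply is that the gap is narrow. A reader might infer that one missed visit removes a subject. The text does not support this: the non-compliance must be significant and persist after calls and letters, and a subject who answers those calls has shown that they are alive. That point stands. The listed efforts aim at attendance, however, and none asks for outcome data in place of a visit.

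A reader might also infer that section 9.5 expressly ends safety follow-up. It does not. Off study is undefined, and the sections on event recording, death reporting and adjudication carry no off-study exception. That stands too. What remains is that no section requires anyone to seek the information.

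A reader might further infer that the 12-month rates will be inflated. The documents do not support that either: the analysis sets in section 9.2 are fixed by crossing or closure attempt, and no passage drops off-study subjects. The 92% and 100% figures above are therefore conditional illustrations and do not show what the plan does.

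Finally, the consequences are limited. The primary endpoint is settled at exit from the laboratory, the analysis is descriptive with no acceptance criterion, and retention is expected to be high. This bears on priority. It does not remove the gap, because late safety of the implant is one of the things the 12-month follow-up is there to describe.

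**Conclusion.** The point holds as a gap in follow-up and reporting. Section 9.5 treats persistent non-attendance like withdrawal, and no section requires active ascertainment of vital status, serious events or device effects afterwards, although sections 9.2.3, 9.2.5, 9.2.6 and 10.2.3 need outcomes to month 12.

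Each subject of unknown status is 6.7 points. For an assumed 1 to 3 losses, the 12-month event proportion is uncertain by up to 6.7 to 20 points. Understatement follows only if the lost subjects are dropped and had events more often than the rest; the plan neither states nor rules out the first, and the second is unknown. The primary endpoint is unaffected. The change is worth making before enrollment because it is cheap and lost outcomes may not be recoverable later.

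**What to change.** In section 9.5, change non-compliance from an off-study criterion to *discontinued from in-person study visits*. State that vital status, reintervention, serious adverse events and device effects are still ascertained to month 12 by telephone, medical records or the primary physician, and through the registry where the subject is enrolled, unless the subject withdraws consent for this. Check that the consent form allows it; the consent pages were not available for this review, so it may already do so.

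In section 9.2, state that all subjects in the defined analysis sets stay in the 12-month denominator. Report those whose status, imaging or laboratory components remain unknown as not evaluable, with a best-case count (e/15 for e observed events) and a worst-case count ((e + m)/15 for m unknown).

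This recovers only part of device success. Survival and known reintervention can be learned remotely, but migration, fracture, hemolysis and pseudoaneurysm rest largely on CT or blood tests, so some subjects will stay not evaluable. The cost is a little coordinator time for at most a few subjects, and a 12-month figure that may look less favourable.
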